Shrinking the Size of the Tobacco Power Wall and Restricting the Number of Tobacco Products Displayed to Reduce Adolescent Tobacco Use

NCT04632030

August 17, 2023

Study Protocol

Study objective. The overall objective of this research is to experimentally evaluate legally viable approaches to reducing the impact of the POS retail environment on adolescent risk of using four classes of tobacco products: cigarettes, ENDS, smokeless tobacco, and LCCs. Specifically, we propose to investigate the extent to which reducing the size of the tobacco powerwall display reduces adolescents' risk of future use of tobacco.

Study design. The experimental conditions that we will compare in this study are: large power wall with a large number of products (status quo/control), small power wall with a small number of products displayed, and a medium sized power wall with a medium number of products displayed. The studies will take place in the RAND StoreLab (RSL), a life-sized replica of a convenience store that was developed to experimentally evaluate how altering aspects of tobacco advertising at POS influences tobacco use.

Methods. The study was approved by the RAND Human Subjects Protection Committee. Young people were recruited from the community through standard advertising campaigns. Interested individuals completed a telephone screening to determine eligibility. Eligible individuals completed informed consent (or consent and assent if minors). Participants completed a baseline questionnaire that assessed demographics, tobacco product cognitions, smoking and tobacco use, and convenience store shopping habits. Participants were then randomized to one of the three experimental conditions. They were provided with a \$10 (fake) RSL gift card and asked to shop in the RSL for whatever they wanted, for as long as they wanted. They were asked to purchase at least one item and check-out and pay for the item(s) as they would in any convenience store. A confederate who was not involved in the consent or survey process served as the cashier. This cashier scanned the selected items for a total price, scanned the gift card, and bagged the items. Although no participants attempted to purchase tobacco from the RSL in this study, any such attempts would have been met by the cashier with a request for age identification and the purchase attempt would have been declined (i.e., because no participants were ≥ 21 years old). After exiting the RSL, participants completed the dependent measures. They then: underwent a graduated debriefing; were asked to guess the study's purpose; and were told that they would be unable to retain the items they selected from the RSL. Participants then viewed a short tobacco media literacy video and received printed smoking prevention materials. Finally, they received a \$40 gift card as compensation.

Statistical analysis plan

First, we evaluated whether randomization distributed pre-shopping baseline characteristics evenly across the experimental conditions. These univariable analyses used either t-tests or chi-squared tests to evaluate significance (depending on variable distribution). Next, we used logistic regression to evaluate the relationship between the experimental conditions and post-RSL shopping risk of using cigarettes; ENDS LCCs, and smokeless tobacco. Lifetime use of each product under investigation was included in the appropriate model as a covariate (0 = no use; 1 = any lifetime use). Finally, because both age (continuous) and education (0 = still in middle/high school; 1 = high

school graduate or more) are related to tobacco use, these variables were also included as covariates. Each reduced tobacco powerwall condition was compared to the all status quo/control condition (reference) using planned contrasts.

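### Does an objective that names only powerwall size, when every arm changes size and number of products together, require a change to the plan?

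*Combined protocol and SAP*

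**What the plan says.** The specific aim in the Study objective section is to "investigate the extent to which reducing the size of the tobacco powerwall display reduces" adolescents' risk of using tobacco in future. The number of products on display is not mentioned in that sentence.

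Elsewhere the document names two features. The title reads "Shrinking the Size of the Tobacco Power Wall and Restricting the Number of Tobacco Products Displayed to Reduce Adolescent Tobacco Use". The Study design section, which comes straight after the objective, describes the control arm as "large power wall with a large number of products (status quo/control" and the two reduced arms as "small power wall with a small number of products displayed, and a medium sized power wall with a medium number of products displayed". Under Methods, "Participants were then randomized to one of the three experimental conditions"; no further arm is described.

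The Statistical analysis plan section takes the condition as its unit of comparison: "we used logistic regression to evaluate the relationship between the experimental conditions and post-RSL shopping risk" for each of the four product classes. It adds: "Each reduced tobacco powerwall condition was compared to the all status quo/control condition (reference) using planned contrasts". No model term or contrast is assigned to size or to number separately.

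**The concern.** Read literally, the objective asks about one feature of the display, and the trial varies two in step. If risk turns out lower in a reduced arm, the smaller wall, the smaller number of products, or both could be responsible. The objective sentence would seem to license a claim about size that the data cannot support.

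This could matter because the study is meant to inform which point-of-sale measures are legally workable. A limit on display size and a limit on the number of products shown can be told apart as measures, and the title itself lists them separately. Neither the objective nor the SAP contains a sentence restricting conclusions to the combination. A reader who went no further than the objective could carry away the wrong attribution.

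**Working it through.** The plan gives no sample size, event rate or effect size that bears on this point, so there is no figure to reproduce. The question is which effects the three arms can identify, and whether the plan claims any others.

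**Step 1: what each arm sets** (Study design section).

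| Arm | Wall size | Number of products |
|---|---|---|
| Status quo (control) | large | large |
| Medium | medium | medium |
| Small | small | small |

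The three possible pairwise comparisons are medium–control, small–control and small–medium. Both features differ in 3 of 3.

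**Step 2: can size be separated from number?** Code size with two indicators (medium, small) and number with two indicators (medium, small), plus an intercept. The rows are:

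- control: (1, 0, 0, 0, 0)
- medium: (1, 1, 0, 1, 0)
- small: (1, 0, 1, 0, 1)

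The second and fourth columns are identical, as are the third and fifth. The 5 columns therefore have rank 3. Size and number are completely aliased. The covariates in the SAP (lifetime use of the product, age, education) are participant characteristics and do nothing to break the aliasing. This part of the concern is correct.

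**Step 3: what do the planned contrasts estimate?** On the log-odds scale, with the covariates held fixed, write s for the effect of changing size alone, n for the effect of changing number alone, and i for any interaction between them:

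- medium versus control = s(medium) + n(medium) + i(medium)
- small versus control = s(small) + n(small) + i(small)

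Each sum is the effect of the whole package. It is estimable from the randomized comparison, and it is the same however the effect divides among its parts. Only the division is unknowable.

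**Step 4: does the plan claim the division?** Set the statements side by side:

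- Title: both features, joined by a conjunction.
- Study design: every arm defined by both features.
- SAP model: the relationship is with the conditions.
- SAP contrasts: each reduced condition against the status quo.
- Study objective: size only.

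Four of these five statements concern the package or the conditions that embody it. One short sentence departs from them, and no analysis is built on its literal reading. An analyst following the SAP would fit the condition indicators and report two contrasts per product, each belonging to a condition already defined by both features.

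**Step 5: what would rewording change?** The arms, randomization, models, contrasts, estimates and tests would all stay as they are. The document also describes conduct and analysis in the past tense, for example "Although no participants attempted to purchase tobacco from the RSL in this study". A revised objective would be a clarification made after the event, repeating what the title and arm definitions already say.

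**The case for a change.** The strongest case for a change is that the objective is where the research question is stated, and disclosure elsewhere does not correct that sentence. As worded, it asks something this trial cannot answer, whereas the contrasts answer a different question. If size was meant as shorthand for the package, nothing in the document says so, and the title and arm descriptions treat the two features as distinct. The remedy would be cheap: one reworded sentence and one line limiting the claim, with no reanalysis.

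Much of this stands. The aliasing is complete, the sentence is narrower than the design, and the shorthand reading is plausible but unconfirmed, since the document gives neither wall dimensions nor product counts. What does not stand is the step from there to a defect in the plan. The document contains no conclusion to correct, and its analysis makes no size-only inference. The harm would arise only if a later report set aside the title and the arm definitions. Bundling the two features is also a legitimate choice when the question is whether a scaled-down display helps at all.

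**Conclusion.** No change to the plan is needed. The objective uses a short label for a manipulation that the title and Study design section spell out in full, and the planned contrasts are valid for that manipulation. The point is minor and confined to wording: no estimate or test is affected. Its numerical consequence cannot be sized from the document, which gives no risks by condition.

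This rests on two things. First, the arms were built as the Study design section describes them, with size and number changing together. Second, whoever reports the results attributes any effect to the conditions as defined, that is, to a smaller wall with fewer products compared with the status quo. A report that credited wall size alone would be open to fair criticism, but the fault would lie in the report and not in this design or analysis.

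### Does checking baseline balance across three arms with t-tests, a two-group test, call for a change to the plan?

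*Combined protocol and SAP*

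**What the plan says.** The Methods paragraph of the protocol says: "Participants were then randomized to one of the three experimental conditions". These are the large (status quo) power wall, the medium one and the small one.

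The Statistical analysis plan opens with the balance check: "First, we evaluated whether randomization distributed pre-shopping baseline characteristics evenly across the experimental conditions". The next sentence names the tests: "These univariable analyses used either t-tests or chi-squared tests to evaluate significance (depending on variable distribution"). No three-group test is named for continuous variables. The plan does not say which pairs a t-test would compare, what significance level applies, or whether there is a multiplicity correction.

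The plan then turns to the outcome models, which are logistic regressions, one for each of four product classes. On covariates it says: "Lifetime use of each product under investigation was included in the appropriate model as a covariate". Age, which is labelled continuous, and a two-level education variable are added, on the stated ground that both are associated with tobacco use. The last sentence sets the comparisons: "Each reduced tobacco powerwall condition was compared to the all status quo/control condition (reference) using planned contrasts".

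**The concern.** Two things look wrong.

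First, the test does not fit the design. A chi-squared test takes three arms at once, but a t-test takes two. For a continuous variable, the stated method can be carried out only as two or three pairwise tests. With no correction stated, a properly randomized variable would then be flagged more often than the nominal rate.

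Second, significance tests of baseline differences are a weak tool after randomization. The null hypothesis they test is true by design. A small p-value does not show that randomization failed. A large one does not show that a variable which predicts the outcome is balanced well enough to ignore. Baseline tobacco product cognitions are the obvious example: they were measured, are probably prognostic, and are not among the listed covariates.

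If the balance check decided which covariates entered the model, or whether the randomization was accepted, over-flagging on one side and false reassurance on the other could reach the trial's conclusions.

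**Working it through.** **Inputs.** The documents give three arms (Methods) and the choice of t-test or chi-squared test (Statistical analysis plan). They give no significance level, sample size, allocation ratio or error rate for this step, so there is no stated figure to reproduce. Assumptions: two-sided 0.05 per test, equal arms, no correction.

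**Step 1: all three pairs.** With equal arms, at least one of the three pairwise tests is significant when the range of three independent standard normal values exceeds q = 1.96 × √2 = 2.772.

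P = 1 − ∫ 3φ(u)[Φ(u + q) − Φ(u)]² du = 0.122.

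The tests share arms and are positively correlated. Treating them as independent would give 1 − 0.95³ = 0.143, which is too high.

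**Step 2: the two comparisons with control only.**

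P = 1 − ∫ φ(u)[Φ(u + q) − Φ(u − q)]² du = 0.091.

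**Step 3: finite samples.** Simulation with 60,000 replicates per setting gave 12.0% to 12.4% for all pairs with 20, 50 and 100 per arm, and 12.2% with unequal arms (120/60/60 and 60/120/60). One-way ANOVA gave 4.9% to 5.1%.

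**Step 4: sensitivity to the assumed level.** For all three pairs the rate is 2.7% at 0.01 and 22.7% at 0.10.

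**Step 5: several variables.** The chance of at least one flag among k independent continuous variables is 1 − (1 − p)^k.

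| k (assumed) | All pairs, p = 0.122 | Three-group test, p = 0.05 |
|---|---|---|
| 1 | 12% | 5% |
| 2 | 23% | 10% |
| 3 | 32% | 14% |
| 10 | 73% | 40% |

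With ten variables and comparisons against control only, the figure is 1 − 0.909¹⁰ = 61%. Age is the only variable the documents label continuous. Lifetime use and education are coded 0/1 and would go to the chi-squared test. The number and scaling of the other questionnaire items are not given, and such items are unlikely to be independent. The ten-variable row is therefore an illustration and not an estimate for this trial.

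**Step 6: does a flag change anything?** Each later decision can be set against its stated basis.

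| Decision | Basis in the plan | Depends on the balance tests? |
|---|---|---|
| Lifetime use in the model | Included for the product concerned, unconditionally | No |
| Age and education in the model | Associated with tobacco use | No |
| Form of the model | Logistic regression | No |
| Comparisons made | Each reduced condition against control, planned | No |
| Exclusions | None tied to balance | No |

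The words that order the steps (first, next, finally) give a sequence. They do not make a later step conditional on an earlier one. Whether the flag rate is 5%, 9% or 12%, the estimates and error rates of the planned contrasts are the same.

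**The case for a change.** The case for a change is a fair one. The sentence is complete, so lost text does not explain it. As written, a second analyst could not reproduce the balance check for age without choosing a procedure. If t-tests is shorthand for analysis of variance, the wording is still inexact. The planned contrasts against control concern outcomes, so they do not settle how baseline was tested. For measured variables outside the model, such as cognitions, the significance test is the only balance assessment described, and it can miss a sizeable difference. Assuming 50 per arm, two arms could differ by up to about 1.98 × √(2/50) = 0.40 SD without reaching 0.05; with 100 per arm, by about 1.97 × √(2/100) = 0.28 SD. The remedy would cost one sentence and a re-run of the baseline table.

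The description of the defect stands: the test is misnamed for three arms, and p-values do not measure prognostic importance. The harm does not follow. An imbalance in cognitions would move a contrast because cognitions are not in the outcome model. That is a question about adjustment, and replacing a t-test with ANOVA, or a p-value with a standardized difference, would not change the contrast. One-way ANOVA would also still be a test of a null that is true by design, and it can miss a pairwise difference that a t-test would flag, so it does not remove the false reassurance. Choosing covariates on prognostic grounds is already the reason the plan gives for age and education, and prior use of the same product is plainly a prognostic variable.

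**Conclusion.** No change to the plan is needed. The mismatch between a two-group test and three arms is real. It would raise the flag rate for a continuous variable with no true difference from about 5% to 12.2% (all pairs) or 9.1% (against control only), assuming two-sided 0.05 and no correction, neither of which the documents state. An analyst with three groups would ordinarily use a three-group test without being told.

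The effect stops at the baseline table. The covariates, model form and contrasts are all fixed on grounds other than the balance tests, so correcting the wording would gain nothing for the trial's conclusions. This rests on reading the covariate list as unconditional, which is what the Statistical analysis plan says. If balance results had in practice been used to add or drop covariates, the point would matter more, but nothing in the documents suggests it.

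### Does the missing 0/1 rule for being at risk of using each product call for a change to the analysis plan?

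*Combined protocol and SAP*

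**What the plan says.** The Study objective is to find out whether "reducing the size of the tobacco powerwall display reduces adolescents' risk of future use of tobacco". The Methods give the timing of measurement but not the instrument: "After exiting the RSL, participants completed the dependent measures". In the Statistical analysis plan, "we used logistic regression to evaluate the relationship between the experimental conditions and post-RSL shopping risk of using cigarettes"; the same sentence goes on to ENDS, LCCs and smokeless tobacco.

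The covariates are described more fully. Lifetime use of the product in question "was included in the appropriate model as a covariate (0 = no use; 1 = any lifetime use"). Age is entered as continuous and education as 0/1, and "these variables were also included as covariates". The comparison is also clear: "Each reduced tobacco powerwall condition was compared to the all status quo/control condition (reference) using planned contrasts".

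The document names no items, response scale, score or cut-off for the outcome. It also gives no effect measure, confidence interval, sample size or significance level. The relevant sentences are complete and show no sign of redaction or broken extraction.

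**The concern.** The outcome is the part of a model that most needs a definition, and here it is the only part without one. Most intention or susceptibility questions have several response levels, so someone must decide which answers count as at risk. Two analysts working only from this text could draw that line in different places and get different event counts, odds ratios and p values.

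Timing adds to the worry. The analysis section is in the past tense and does not say when the rule was set. If it was set before the outcome data were seen, each test keeps its nominal level. If several rules were tried and the most favourable kept, it does not. With four products and two reduced conditions there are 4 × 2 = 8 contrasts, all of which depend on the rule. The objective also asks about the extent of an effect, so leaving the effect measure and interval unnamed looks like a second omission.

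**Working it through.** The plan has no figure to reproduce: it states no sample size, power, event rate or effect size. The check is therefore a reading of the text, followed by an illustration on assumed inputs.

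**Reading the text**

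- *Outcome type.* Logistic regression without a qualifier ordinarily means a binary outcome. Nothing in the document points to an ordinal model.
- *Effect measure.* Logistic regression with contrasts against a reference condition gives log odds ratios adjusted for lifetime use, age and education. The odds ratio and its interval come from the same fit.
- *Existence of a rule.* The document reports the models as already fitted. Fitting them requires a 0/1 variable for each product, so a rule existed for each.
- *Link to future use.* The objective concerns risk of future use, not observed use, so measuring just after shopping does not contradict it. Whether the answers predict later use depends on the validity of the items, which stating a cut-off would not settle.

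**Illustration: how much could the rule matter?**

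Assumed inputs, none from the document: a normally distributed underlying score; rules that class p = 10%, 30% or 50% of controls as at risk; a true shift d = 0.30 SD; 100 or 200 participants per arm; a two-sided 5% test.

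With z the normal quantile at 1 − p, the share at risk in a reduced condition is p1 = 1 − Φ(z + d). The odds ratio is OR = [p1/(1 − p1)] / [p/(1 − p)]. The standard error satisfies SE² = 1/(np) + 1/(n(1 − p)) + 1/(np1) + 1/(n(1 − p1)). Power = Φ(|ln OR|/SE − 1.96) + Φ(−|ln OR|/SE − 1.96).

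| p | p1 | OR | Risk difference (points) | Power, n = 100 | Power, n = 200 |
|---|---|---|---|---|---|
| 0.10 | 0.0569 | 0.54 | −4.3 | 20% | 35% |
| 0.30 | 0.2049 | 0.60 | −9.5 | 34% | 59% |
| 0.50 | 0.3821 | 0.62 | −11.8 | 39% | 66% |

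All three rules point the same way and the odds ratios are close. Their spread comes from the normal assumption: if the underlying score is logistic and simply shifted, the odds ratio is the same at every cut. For example, at OR = 0.60 and p = 0.10 the odds are 0.1111 × 0.60 = 0.0667, so p1 = 0.0667/1.0667 = 0.0625; at p = 0.50 they are 1 × 0.60, so p1 = 0.60/1.60 = 0.375. The differing risk differences and power reflect different binary outcomes, and would arise just as much if every rule were fully written down.

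**Type I error**

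With one rule fixed in advance, the level is 5% per contrast. If the most significant of several rules is kept, the test statistics for cuts p < q have null correlation √[p(1 − q)/(q(1 − p))], and the error is P(max|Z| > 1.96):

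| Rules tried | Type I error |
|---|---|
| 10%, 30% (correlation 0.51) | 9.0% |
| 10%, 50% (correlation 0.33) | 9.5% |
| 30%, 50% (correlation 0.65) | 8.5% |
| all three | 12.3% |

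These large-sample values do not depend on n. They are upper limits per contrast, since they let each contrast choose its own best rule. One rule applied across all contrasts could not be expected to be the best choice for every one.

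**The case for a change.** The strongest case for asking for a change is that brevity does not explain the gap. The authors had room to say how every covariate is coded, yet left the outcome of all four models undefined. Knowing that the outcome is binary does not tell a reader who falls on which side. The closest candidate, the baseline questions on product cognitions, is neither defined nor tied to the outcome. In simulated adjusted models with 100 per arm and the 0.30 SD shift, the 30% and 50% rules disagreed on significance in 29% of trials. The remedy would be a few sentences.

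The factual part of this stands: the outcome cannot be rebuilt from this document alone, and a reader cannot tell when the rule was set. The inference to a faulty analysis does not. The 29% arises where simulated power is only 36% and 43%, so many results lie near the significance threshold, and the sample size is an assumption. The inflated error rates require selection among rules, and past-tense wording is not evidence of it. The remaining requests, for a named odds ratio with an interval and for standardized risks, are reporting preferences that alter no planned test.

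**Conclusion.** No change to the plan follows. The document leaves out, for each of four products, the items and the rule behind the at-risk classification, and does not say when that rule was set. This is missing description of something the investigators must have had in order to fit the models; it does not show an error in the model, covariates or contrasts. Writing the rule down would help a reader, and the trial report is a natural place for it, but it would leave every planned analysis as it is.

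The consequence cannot be quantified from the document. The type I error range, from 5% for a rule fixed in advance to 12.3% for the best of three rules chosen per contrast, rests on assumed cut-offs and, above 5%, on selection that nothing in the text indicates. The odds ratios of 0.54 to 0.62 and the power figures also assume a normal score, a 0.30 SD shift and an invented sample size. They show that the choice of rule can matter, not that it went wrong here. The conclusion would differ if there were evidence that the rule was chosen after the outcome data were examined; the document contains none.

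### Tobacco cognitions measured before randomization are left out of the outcome models: no bias, but a possible loss of power whose size the documents do not fix

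*Combined protocol and SAP*

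**What the plan says.** Four statements in the Methods and the Statistical analysis plan settle the facts.

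- **Measured.** "Participants completed a baseline questionnaire that assessed demographics, tobacco product cognitions, smoking and tobacco use, and convenience store shopping habits" (Methods).
- **Timing.** "Participants were then randomized to one of the three experimental conditions" (Methods, directly after the questionnaire). The outcomes come later: "After exiting the RSL, participants completed the dependent measures".
- **Outcome models.** There is one logistic regression per product class. On the first covariate the plan says "Lifetime use of each product under investigation was included in the appropriate model as a covariate". Age and education follow, on the ground that they "are related to tobacco use, these variables were also included as covariates". The covariate list ends there.
- **Other use of baseline data.** The only other use stated is a balance check: "we evaluated whether randomization distributed pre-shopping baseline characteristics evenly across the experimental conditions", by t-test or chi-squared test. No rule links that check to the choice of covariates.

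The documents do not list the cognition items, say which of the four products they cover, or say whether any item repeats a post-shopping risk item. They also give no sample size, significance level, event rate or effect size.

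**The concern.** In a randomized comparison, a covariate measured before allocation can be adjusted for without risk of conditioning on a consequence of treatment. If it predicts the outcome, adjustment raises the chance of detecting a true effect. What people think about tobacco products before shopping is a plausible predictor of their risk of use after shopping. The plan's own reason for including age and education, their relation to tobacco use, would seem to apply to cognitions too, and no reason is given for leaving them out. At stake is power to detect an effect of shrinking the powerwall. The validity of the test is not in question.

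**Working it through.** The plan states no power or sample size, so there is no figure to reproduce. Every input below is an assumption.

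**1. A calculation that can be followed by hand.** Assume 150 per arm, a two-sided 5% test, control risk 0.40 and a marginal odds ratio of 0.5, so the risk in the reduced-display arm is 0.25. Power is Φ(|log OR|/SE − 1.96).

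Without the score:
- SE = √[1/(150×0.40×0.60) + 1/(150×0.25×0.75)] = √(0.0278 + 0.0356) = 0.252.
- Power = Φ(0.693/0.252 − 1.96) = 78.6%.

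With a standard-normal score whose log odds ratio is g per SD, and the marginal risks held fixed, the conditional odds ratio moves away from 1 and its SE also rises:

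| g | Conditional OR | SE | Power | Gain (points) |
|---|---|---|---|---|
| 0 | 0.500 | 0.252 | 78.6% | 0 |
| 0.5 | 0.482 | 0.259 | 80.5% | 1.9 |
| 1 | 0.438 | 0.277 | 84.6% | 6.0 |
| 1.5 | 0.383 | 0.301 | 89.0% | 10.4 |
| 2 | 0.328 | 0.329 | 92.4% | 13.8 |

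At g = 1, for example, |log 0.438| = 0.825 and Φ(0.825/0.277 − 1.96) = 84.6%. The score's correlation with the outcome in the control arm is g·E[p(1−p)]/√(0.40×0.60). At g = 0.5 this is 0.5×0.227/0.490 = 0.23, and at g = 1 it is 1×0.199/0.490 = 0.41.

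**2. Simulation with the plan's covariates.** There were 4,000 three-arm trials per cell and a two-sided 5% Wald test of small display against control. The stated model has arm, lifetime use, age and education; the expanded model adds a continuous score.

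Assumed throughout: lifetime use 30%, age log-OR 0.2 per SD, education a noisy threshold of age, and medium-arm risk midway. In the weak setting, lifetime use has log-OR 1.0 and latent correlation 0.3 with cognition; in the strong setting these are 2.0 and 0.6. The index is the score's partial correlation with the outcome given the stated covariates.

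Gain in power in points, weak / strong, taken from powers rounded to three decimals:

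| Per arm; control vs small | Partial 0.2 | 0.3 | 0.4 | 0.5 |
|---|---|---|---|---|
| 150; 42% vs 37% | 0.3 / 0.8 | 1.0 / 0.7 | 1.7 / 3.3 | 3.3 / 6.9 |
| 150; 42% vs 31% | 2.0 / 1.5 | 3.6 / 4.0 | 8.2 / 8.5 | 14.1 / 14.8 |
| 150; 42% vs 27% | 1.6 / 0.5 | 3.3 / 2.0 | 5.9 / 4.3 | 9.6 / 7.1 |
| 150; 25% vs 16% | 0.8 / 2.3 | 4.5 / 5.9 | 8.2 / 10.9 | 12.7 / 19.3 |
| 150; 12% vs 4% | 1.2 / 2.7 | 4.6 / 7.0 | 9.8 / 14.0 | 17.3 / left out |
| 75; 42% vs 28% | 1.3 / 1.6 | 2.9 / 4.2 | 6.6 / 7.2 | 11.6 / 15.1 |

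- At partial correlation 0 the gain lies between −0.3 and 0.3 points, and at 0.1 between −0.2 and 0.8.
- At 42% vs 22% with 150 per arm, stated power is already about 97% or more and the gain never exceeds 1.8.
- The Monte Carlo SE of a gain is at most 0.7 points.
- The cell left out had a score log-OR of 6.6, and 235 to 1,142 of 4,000 fits failed. Elsewhere at most 46 failed, all at 12% control risk.

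The weak and strong columns nearly agree at 42% vs 31% but diverge at lower event rates. The partial correlation alone therefore does not fix the gain.

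**3. Bias and type I error.** With no true effect, the stated model rejected in 4.2 to 5.3% of trials and the expanded model in 4.3 to 5.6%. A separate run of 2,000 trials per setting gave 4.5 to 6.6% and 4.6 to 6.1% (Monte Carlo SE about 0.5 points). Its highest values came from the same setting in both models, so they do not point to the omission. The mean null odds ratio from the stated model in that run was 0.99 to 1.00.

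**4. Change of meaning.** In the same separate run, a cognition-conditional odds ratio of 0.5 appeared in the stated model as about 0.51, 0.55, 0.61 and 0.66 at g = 0.5, 1, 1.5 and 2. This is non-collapsibility of the odds ratio, not confounding.

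**The case against.** The strongest reply is that the plan contains no defect. It already adjusts for a product-specific behavioural predictor plus age and education, and gives a reason for the last two. A further covariate is partly a matter of preference. The Methods name the cognition measure without items, products or scale, and nothing places its partial correlation at 0.3 to 0.5 rather than 0 to 0.2. The plan is also written in the past tense, so the analysis may be complete, and a second model run afterwards adds no power to it. It would add eight comparisons (four products by two contrasts). All of this stands, and it limits the point to an optional improvement.

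A reader might be tempted further, in four ways that the documents do not support:

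- **That the omission biases the powerwall comparison.** Randomization rules out systematic confounding, and the null simulations agree.
- **That a baseline version of the outcome was collected and ignored.** The documents do not say that the cognition items repeat the risk items.
- **That the loss is as large as the right-hand columns of the table.** Those need a very strong predictor, which is unconfirmed.
- **That the loss is negligible whenever power is low.** In the 42% vs 37% row, where stated power is 15 to 19%, the gain at partial correlation 0.5 is still 3.3 to 6.9 points.

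**Conclusion.** The point holds as a modest, conditional matter of efficiency. A pre-randomization measure is available and unused. The stated model remains valid and unbiased for its own odds ratio, with no inflation of type I error.

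The cost in power is about 0 to 3 points if the score's partial correlation is 0.2 or less and about 1 to 7 points at 0.3. It is less where power is already about 97% or more. It also varies with the event rate and with how strongly lifetime use predicts the outcome. These figures rest wholly on assumed arm sizes, risks and associations; the documents supply none. The point is a cheap improvement.

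**What to change.** - State which cognition items were asked at baseline and for which products.
- Add that product's pre-shopping cognition score to its logistic model, using the baseline version of the outcome if it was asked. Keep lifetime use, age and education.
- Set one rule in advance for all four products: for example, the expanded model for every product that has a score, fitted by penalised likelihood if events are sparse. Do not choose the model by whether it converges.
- Report the stated model beside the expanded one for every product, with the score's coefficient so that readers can see what it adds.
- Note that the expanded odds ratio is more conditional. It is not interchangeable with the stated one, nor comparable across products whose models hold different covariates.
- If outcomes have already been analysed, label the expanded model a post hoc sensitivity analysis and claim no added power for the stated analysis.

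No new data are needed. The cost is a second set of odds ratios with a more conditional meaning, and some care over sparse events.
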